- Vital signs: temperature (oral, tympanic or temporal preferred), BP and PR. For subjects with sJIA: temperature must be measured orally using a digital thermometer, with the exception of very young children or others who cannot tolerate an oral thermometer. In these cases temperature may be measured rectally using a digital thermometer. The definition of fever with a rectal thermometer is one degree Fahrenheit higher. (Example >101.4°F/38.6°C rectally compared to >100.4°F/38°C orally).
- Complete physical examination. (**Applicable to Investigative Sites in the UK and Belgium:** a full skin cancer examination must be performed as part of the complete physical examination. **Applicable to subjects enrolled from Study A3921165:** a skin examination for chicken pox or shingles must be performed).
- Tanner stage assessment.
- Physician global evaluation of disease activity.
- Joint assessment of active arthritis (swelling, pain/tenderness), and limitation of motion.
- Duration of morning stiffness.
- QuantiFERON® Gold or Gold Plus In-Tube test (QFT) performed annually: ONLY for subjects enrolled in countries where TB incidence has been reported at a rate of >50 cases per 100,000 persons, eg, China, Russian Federation; South Africa, India and Ukraine. (World Health Organization). Sites must perform chest radiograph for TB status determination when subjects have a positive annual QFT-TB test for the first time. Refer to [Section 7.2.2](#) for further guidance.
- Safety laboratory testing (chemistry, hematology, urinalysis), including urine pregnancy testing (β-hCG) for females of child-bearing potential.
- Confirm highly effective contraception is being used.
- Lipid panel (cholesterol, indirect LDL, direct HDL, apolipoprotein A-1 and B, triglycerides).

***** Important Note ** Subjects should be instructed to fast (for 9 to 12 hours prior the scheduled visit), if possible, for lipid panel testing.***
- CRP.
- ESR determination (Westergren method).

- Uveitis exam performed by an ophthalmologist (or qualified equivalent per local practice) annually (the window for this particular examination is ± 30 days). Refer to [Section 7.2.5](#) for further guidance.
- Assess investigational product dosing compliance.
- Dispense/collect study medication/schedule next visit.

sJIA subjects ONLY:

- Assessment of JIA-associated fever: Fever is defined as temperature $>38^{\circ}\text{C}/100.4^{\circ}\text{F}$. Refer to [Section 7.1.10.1](#) for details.
- MAS diagnosis: Only if subject has fever and Macrophage Activation Syndrome (MAS) is suspected: obtain blood samples to evaluate ferritin, platelets, triglycerides and fibrinogen levels. Refer to [Section 7.2.9](#) for details regarding these blood sample collections.
- Assess extra-articular sJIA manifestations: rash, serositis, splenomegaly, hepatomegaly, or generalized lymphadenopathy attributable to sJIA.

ERA subjects ONLY:

- Tender Entheseal Assessment.
- Modified Schober's Test.
- Overall Back Pain.
- Nocturnal Back Pain Assessment.

PsA subjects ONLY:

- Body surface area (BSA) with psoriasis rash.
- Physician's Global Assessment (PGA) for psoriasis.

Applicable to Canadian Investigator Sites Only: Calculate the subject's ACR30 response (see [Section 7.1.6.1](#)) at each visit. Subjects with less than an ACR30 response for 2 consecutive visits, beginning with the Month 3 visit and anytime thereafter, should be discontinued from study treatment, unless, in the opinion of the Investigator, it is in the subject's best interest to continue receiving tofacitinib (to be determined on a case-by-case basis and in consultation with the Sponsor).

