- Lipid panel (total cholesterol, indirect LDL, direct HDL, apolipoprotein A-1 and B, triglycerides) done at Months 6 and 12.

***** Important Note ** Subjects should be instructed to fast (for 9 to 12 hours prior the scheduled visit), if possible, for lipid panel testing at Month 6 and Month 12 visits.***

- CRP.
- ESR determination (Westergren method).
- PK blood samples (pre-dose, and post dose at 0.5 hr [time window: 0.25-0.75 hr] and 2 hr [time window: 1.75-2.5 hr]) obtained at Month 12.

***** Important Note ** Subject and parent/legal guardian should be instructed that the subject should NOT take the morning dose at home. The subject's morning dose will be taken at the study site after pre-dose PK sampling.***

- Uveitis exam performed by an ophthalmologist (or qualified equivalent per local practice) annually beginning 1 year after the previous exam (the window for this particular examination is ± 30 days). Refer to [Section 7.2.5](#) for further guidance.
- Assess investigational product dosing compliance.
- Dispense/collect study medication/schedule next visit.

sJIA subjects ONLY:

- Assessment of JIA-associated fever: Fever is defined as temperature $>38^{\circ}\text{C}/100.4^{\circ}\text{F}$. Refer to [Section 7.1.10.1](#) for details.
 - MAS diagnosis: Only if subject has fever and Macrophage Activation Syndrome (MAS) is suspected: obtain blood samples to evaluate ferritin, platelets, triglycerides and fibrinogen levels. Refer to [Section 7.2.9](#) for details regarding these blood sample collections.
- Assess extra-articular sJIA manifestations: rash, serositis, splenomegaly, hepatomegaly, or generalized lymphadenopathy attributable to sJIA.

090177e19a2c798c\Approved\Approved On: 18-May-2022 13:36 (GMT)

ERA subjects ONLY (Months 3, 6, and 12):

- Tender Enthesal Assessment.
- Modified Schober's Test.
- Overall Back Pain.
- Nocturnal Back Pain Assessment.

PsA subjects ONLY (Months 3, 6, and 12):

- Body surface area (BSA) with psoriasis rash.
- Physician's Global Assessment (PGA) for psoriasis.

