- QuantiFERON® Gold or Gold Plus In-Tube test (QFT) performed annually: ONLY for subjects enrolled in countries where TB incidence has been reported at a rate of >50 cases per 100,000 persons, eg, China, Russian Federation; South Africa, India and Ukraine. (World Health Organization). Sites must perform chest radiograph for TB status determination when subjects have a positive annual QFT-TB test for the first time. Refer to [Section 7.2.2](#) for further guidance.
- Safety laboratory testing (chemistry, hematology, urinalysis), including urine pregnancy testing (β -hCG) for females of child-bearing potential.
- Confirm highly effective contraception is being used.
- Lipid panel (total cholesterol, indirect LDL, direct HDL, apolipoprotein A-1 and B, triglycerides) done at Months 18, 24, 30, 36, 42, 48, 54, and 60.

***** Important Note ** Subjects should be instructed to fast (for 9 to 12 hours prior the scheduled visit), if possible, for lipid panel testing.***

- CRP.
- ESR determination (Westergren method).
- PK blood samples (pre-dose, and post dose at 0.5 hr [time window: 0.25-0.75 hr] and 2 hr [time window: 1.75-2.5 hr]) obtained at Months 24 and 36.

***** Important Note ** Subject and parent/legal guardian should be instructed that the subject should NOT take the morning dose at home. The subject's morning dose will be taken at the study site after pre-dose PK sampling.***

- Uveitis exam performed by an ophthalmologist (or qualified equivalent per local practice) annually (the window for this particular examination is ± 30 days). Refer to [Section 7.2.5](#) for further guidance.

- Assess investigational product dosing compliance.
- Dispense/collect study medication/schedule next visit.

sJIA subjects ONLY:

- Assessment of JIA-associated fever: Fever is defined as temperature $>38^{\circ}\text{C}/100.4^{\circ}\text{F}$. Refer to [Section 7.1.10.1](#) for details:
 - MAS diagnosis: Only if subject has fever and Macrophage Activation Syndrome (MAS) is suspected: obtain blood samples to evaluate ferritin, platelets, triglycerides and fibrinogen levels. Refer to [Section 7.2.9.1](#) for details regarding these blood sample collections.
- Assess extra-articular sJIA manifestations: rash, serositis, splenomegaly, hepatomegaly, or generalized lymphadenopathy attributable to sJIA.

ERA subjects ONLY (Months 18, 24, 30, 36, 42, 48, 54, and 60):

- Tender Enthesal Assessment.
- Modified Schober's Test.
- Overall Back Pain.
- Nocturnal Back Pain Assessment.

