
PsA subjects ONLY (Months 18, 24, 30, 36, 42, 48, 54, and 60):

- Body surface area (BSA) with psoriasis rash.
- Physician's Global Assessment (PGA) for psoriasis.

Applicable to Canadian Investigator Sites Only: Calculate the subject's ACR30 response (see [Section 7.1.6.1](#)) at each visit. Subjects with less than an ACR30 response for 2 consecutive visits, beginning with the Month 3 visit and anytime thereafter, should be discontinued from study treatment, unless, in the opinion of the Investigator, it is in the subject's best interest to continue receiving tofacitinib (to be determined on a case-by-case basis and in consultation with the Sponsor).

6.2.3. Years 6-10: Month 63, 66, 69, 75, 78, 81, 87, 90, 93, 99, 102, 105, 111, 114, 117 Visits (Visit Window ± 10 Days)

The following procedures and assessments will be performed:

- AE assessment.
- Risk factor check for venous thromboembolism (see [Section 7.2.10](#)).

- Document concomitant medications (ongoing or started since previous visit).
- Childhood Health Assessment Questionnaire (CHAQ).
- Vital signs: temperature (oral, tympanic or temporal preferred), BP and PR. For subjects with sJIA: temperature must be measured orally using a digital thermometer, with the exception of very young children or others who cannot tolerate an oral thermometer. In these cases temperature may be measured rectally using a digital thermometer. The definition of fever with a rectal thermometer is one degree Fahrenheit higher. (Example >101.4°F/38.6°C rectally compared to >100.4°F/38°C orally).
- Targeted physical examination.
(**Applicable to subjects enrolled from Study A3921165:** a skin examination for chicken pox or shingles must be performed).
- Physician global evaluation of disease activity.
- Joint assessment of active arthritis (swelling, pain/tenderness), and limitation of motion.
- Duration of morning stiffness.
- QuantiFERON® Gold or Gold Plus In-Tube test (QFT) performed annually: ONLY for subjects enrolled in countries where TB incidence has been reported at a rate of >50 cases per 100,000 persons, eg, China, Russian Federation; South Africa, India and Ukraine. (World Health Organization). For subjects who have a positive annual QFT-TB for the first time, sites must perform chest radiograph for TB status determination. Refer to [Section 7.2.2](#) for further guidance.

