6.2.5. End of Study Visit/Early Termination Visit

The following procedures and assessments will be performed:

- AE assessment.
- Risk factor check for venous thromboembolism (see [Section 7.2.10](#)).
- Document concomitant medications (ongoing or started since previous visit).
- Childhood Health Assessment Questionnaire (CHAQ).
- Vital signs: temperature (oral, tympanic or temporal preferred), BP and PR. For subjects with sJIA: temperature must be measured orally using a digital thermometer, with the exception of very young children or others who cannot tolerate an oral thermometer. In these cases temperature may be measured rectally using a digital thermometer. The definition of fever with a rectal thermometer is one degree Fahrenheit higher. (Example >101.4°F/38.6°C rectally compared to >100.4°F/38°C orally).

Complete physical examination. (**Applicable to Investigative Sites in the UK and Belgium:** a full skin cancer examination must be performed as part of the complete physical examination. **Applicable to subjects enrolled from Study A3921165:** a skin examination for chicken pox or shingles must be performed).

- Tanner stage assessment.
- Physician global evaluation of disease activity.
- Joint assessment of active arthritis (swelling, pain/tenderness), and limitation of motion.
- Duration of morning stiffness.
- Safety laboratory testing (chemistry, hematology, urinalysis), including urine pregnancy testing (β -hCG) for females of child-bearing potential.
- Confirm highly effective contraception is being used.
- Please note: Subjects must use contraception consistently and correctly for at least 28 days after the last dose of investigational product.
- Lipid panel (cholesterol, indirect LDL, direct HDL, apolipoprotein A-1 and B, triglycerides).

***** Important Note ** Subjects should be instructed to fast (for 9 to 12 hours prior the scheduled visit), if possible, for lipid panel testing.***

- CRP.
- Erythrocyte sedimentation rate (ESR) determination (Westergren method).
- PK blood samples (pre-dose, and post-dose at 0.5 hr [time window: 0.25-0.75 hr] and 2 hr [time window: 1.75-2.5 hr] if early termination occurs within 36 months).

***** Important Note ** Subject and parent/legal guardian should be instructed that the subject should NOT take the morning dose at home. The subject's morning dose will be taken at the study site after pre-dose PK sampling.***

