- Uveitis exam performed by an ophthalmologist (or qualified equivalent per local practice) (the window for this particular examination is ± 30 days).
- Collect study medication.

Assess investigational product dosing compliance **sJIA subjects ONLY:**

- Assessment of JIA-associated fever: Fever is defined as temperature $>38^{\circ}\text{C}/100.4^{\circ}\text{F}$. Refer to [Section 7.1.10.1](#) for details.
- MAS diagnosis: Only if subject has fever and Macrophage Activation Syndrome (MAS) is suspected: obtain blood samples to evaluate ferritin, platelets, triglycerides and fibrinogen levels. Refer to [Section 7.2.9](#) for details regarding these blood sample collections.
- Assess extra-articular sJIA manifestations: rash, serositis, splenomegaly, hepatomegaly, or generalized lymphadenopathy attributable to sJIA.

ERA subjects ONLY: Tender Entheses Assessment, Modified Schober's Test, Overall Back Pain and Nocturnal Back Pain Assessment.

PsA subjects ONLY: Body surface area (BSA) with psoriasis rash and Physician's Global Assessment (PGA) for psoriasis.

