## 6.2. Secondary Endpoints

All efficacy endpoints are secondary and listed in [Section 3.2](#). [Table 2](#) summarizes the analysis sets to be used in the analysis of each efficacy endpoint.

The secondary efficacy endpoints will be summarized using descriptive statistics by visit for the binary and continuous endpoints respectively. The percent (for the binary endpoints) and mean change (for the continuous endpoints) over time and associated standard errors will be plotted for analyses in sJIA1, sJIA2 and pJIA analysis sets (see [Table 2](#)).

The binary endpoints are JIA ACR responses, occurrence of JIA ACR disease flare, JIA ACR clinical inactive disease status and clinical remission, occurrence of JADAS minimum disease activity and inactive disease, eligibility of tapering, partial tapering success and complete tapering success for corticosteroids, MTX/leflunomide, and tofacitinib, absence of fever for sJIA subjects at each visit. Number, frequency, percent and the associated standard error will be presented for binary variables. JIA ACR disease flare will only be summarized for those who have reached Month 3 Visit of this extension study.

The continuous endpoints are change from baseline in physician global evaluation of disease activity, number of joints with active arthritis, number of joints with limitation of motion, CRP, ESR, CHAQ, JADAS-27 CRP, JADAS-27 ESR at each visit. Number, mean, standard deviation, standard error of the mean, median, quartiles, minimum, and maximum will be presented for continuous variables.

For ERA subjects, change from baseline in TEA, Modified Schober's Test, Overall Back Pain, Nocturnal Back Pain at each visit will be summarized as continuous variables.

For PsA subjects, change from baseline in BSA affected by psoriasis, PGA of psoriasis at each visit will be summarized as continuous variables.

For ESR and any efficacy endpoint summaries involving ESR, all ESR data points including those collected with expired/non-standard ESR kits will be used for analysis. Supportive analyses will be performed to evaluate the impact of expired/non-standard ESR kits (see Section 6.2.1).

For CHAQ and any efficacy endpoint summaries (i.e., JIA ACR responses, JIA ACR flare, and JADAS) involving CHAQ, subjects with invalid CHAQ measurements will be excluded for the visits where these invalid measurements were made. Examples of invalid CHAQ measurements include:

- incorrectly translated CHAQ data

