**Appendix 1.12. Definition and Use of Visit Windows in Reporting**

Visit windows will be used for efficacy variables, and for any safety displays that display by visit. If more than one observation from the same subject falls into the same visit window, the value closest to the targeted day will be used as the observation for that visit. If there are two days having the same distance from target day, the earlier day will be used. All observations will, however, be included in the listings.

Visit Label	Target Day	Definition [Day window]
Baseline	Day 1	Day 1
Month 1	Day 30	Days 2-60
Month 3	Day 90	Days 61-135
Month 6	Day 180	Days 136-225
Month 9	Day 270	Days 226-317
Month 12	Day 360+5=365	Days 318-410
Month 15	Day 450+5=455	Days 411-500
Month 18	Day 540+5=545	Days 501-590
Month 21	Day 630+5=635	Days 591-683
Month 24	Day 720+10=730	Days 684-775
Month 27	Day 810+10=820	Days 776-865
Month 30	Day 900+10=910	Days 866-955
Month 33	Day 990+10=1000	Days 956-1048
Month 36	Day 1080+15=1095	Days 1048-1140
Month 39	Day 1170+15=1185	Days 1141-1230
Month 42	Day 1260+15=1275	Days 1231-1320
Month 45	Day 1350+15=1365	Days 1321-1413
Month 48	Day 1440+20=1460	Days 1414-1505
Month 51	Day 1530+20=1550	Days 1506-1595
Month 54	Day 1620+20=1640	Days 1596-1685
Month 57	Day 1710+20=1730	Days 1686-1778
Month 60	Day 1800+25=1825	Days 1779-1870
Month 63	Day 1890+25=1915	Days 1871-1960

Visit Label	Target Day	Definition [Day window]
Month 66	Day 1980+25=2005	Days 1961-2050
Month 69	Day 2070+25=2095	Days 2051-2143
Month 72	Day 2160+30=2190	Days 2144-2235
Month 75	Day 2250+30=2280	Days 2236-2325
Month 78	Day 2340+30=2370	Days 2326-2415
Month 81	Day 2430+30=2460	Days 2416-2508
Month 84	Day 2520+35=2555	Days 2509-2600
Month 87	Day 2610+35=2645	Days 2601-2690
Month 90	Day 2700+35=2735	Days 2691-2780
Month 93	Day 2790+35=2825	Days 2781-2873
Month 96	Day 2880+40=2920	Days 2874-2965
Month 99	Day 2970+40=3010	Days 2966-3055
Month 102	Day 3060+40=3100	Days 3056-3145
Month 105	Day 3150+40=3190	Days 3146-3238
Month 108	Day 3240+45=3285	Days 3239-3330
Month 111	Day 3330+45=3375	Days 3331-3420
Month 114	Day 3420+45=3465	Days 3421-3510
Month 117	Day 3510+45=3555	Days 3511-3603
Month 120 a	Day 3600+50=3650	≥ Days 3604

a: Additional visits may be added depending on the actual total duration of the study.

For the summary of Tanner Stage, the following visit windows will be used.

Visit Label	Target Day	Definition [Day window]
Baseline	Day 1	Day 1
Month 12	Day $360+5=365$	Days 2-547

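### ERA, PsA and lipid values taken at the exit visit fall into 3-month windows where nothing is scheduled: 20 of 41 columns for ERA/PsA and 26 of 41 for lipids

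*Protocol*

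**What the plan says.** **Schedule.** In Year 1 the protocol lists "ERA subjects ONLY (Months 3, 6, and 12", with the same months for PsA. For Years 2 to 5 it lists "ERA subjects ONLY (Months 18, 24, 30, 36, 42, 48, 54, and 60" and "PsA subjects ONLY (Months 18, 24, 30, 36, 42, 48, 54, and 60". In Years 6 to 10 the ERA/PsA measures continue at 6-month spacing (Sections 6.2.3 and 6.2.4). Lipids are taken at Months 6 and 12, every 6 months to Month 60, then at Months 72, 84, 96, 108 and 120.

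**Exit visit.** Protocol Section 6.2.5 repeats all of these at End of Study/Early Termination, with no restriction to scheduled months. Its list includes "PsA subjects ONLY: Body surface area (BSA) with psoriasis rash", the ERA measures, and "Lipid panel (cholesterol, indirect LDL, direct HDL, apolipoprotein A-1 and B, triglycerides".

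**Analysis.** SAP 6.2 states for PsA that "change from baseline in BSA affected by psoriasis, PGA of psoriasis at each visit will be summarized as continuous variables", and treats the ERA measures the same way. SAP 6.1 presents safety data by visit. Appendix 1.12 states that "Visit windows will be used for efficacy variables, and for any safety displays that display by visit", and gives one general table: Month 1, then every 3 months from Month 3 to Month 120. If two values share a window, the one closer to the target day is kept. The only assessment with its own table is Tanner Stage: "For the summary of Tanner Stage, the following visit windows will be used". SAP 5.3 does not impute these measures. No rule says how exit records are displayed.

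**The concern.** A child who stays in the study has no planned ERA, PsA or lipid value in windows such as Months 1, 9, 15, 21 or 27. A child who exits in one of those windows does. Followed as written, the by-visit tables alternate between columns covering nearly everyone still on study and columns covering only children at their last visit.

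The secondary objective is persistence of efficacy, and lipids belong to the primary laboratory endpoint. A reader following mean change in tender entheses, back pain, BSA, PGA or LDL across columns would meet changes of population that look like changes over time. The number evaluated shows that a column is small. It does not show that the column consists of exits.

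This differs from an exit value competing with a scheduled one, because in these windows no scheduled value exists.

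**Working it through.** The documents give no figure on this point, so the check is a count.

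**1. Windows without a scheduled assessment.** Appendix 1.12 has 41 post-baseline windows (Month 1, plus Months 3 to 120 in steps of 3: 1 + 40). Matched to protocol Sections 6.2.1 to 6.2.4:

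| Period | Windows | ERA/PsA unscheduled | Lipids unscheduled |
|---|---|---|---|
| Year 1 | 5 | 2 | 3 |
| Years 2-5 | 16 | 8 | 8 |
| Through Month 60 | 21 | 10 (47.6%) | 11 (52.4%) |
| Years 6-10 | 20 | 10 | 15 |
| All | 41 | 20 (48.8%) | 26 (63.4%) |

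The ERA/PsA windows are Months 1, 9, 15, 21 and so on to 117. For lipids they are Months 1, 3, 9, 15 and so on to 57, then every non-annual visit.

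**2. Share of study days to Day 1870** (1,869 days; Day 1048, which the SAP lists in two windows, is counted under Month 33).
- The eight windows from Month 15 to Month 57 cover 4 × 90 + 4 × 93 = 732 days.
- ERA/PsA: add Month 1 (59) and Month 9 (92). 883/1,869 = 47.2%.
- Lipids: add Month 3 (75). 958/1,869 = 51.3%.

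**3. Drift.** The protocol counts 30-day months, while SAP target days add 5 days per year.
- Through Month 84, every visit within ±10 days stays in its own window. The unscheduled counts there are 14 of 29 (ERA/PsA) and 17 of 29 (lipids).
- From Month 87, early visits can slip back one window.
- An on-time Month 114 visit (Day 3420) falls in the Month 111 window (Days 3331-3420). An on-time Month 120 visit (Day 3600) falls in the Month 117 window (Days 3511-3603).

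So a few of the latest "unscheduled" columns can hold scheduled values.

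**4. Children per column (illustration).** Protocol Section 2.3.2 reports 227 enrolled, 2 untreated and 177 ongoing at the June 2019 cutoff, so 227 − 2 − 177 = 48 had left. The documents do not give the timing of these exits. Assume even spread and one lipid panel per exit:
- over 2 years: 48 × 409/730 = 26.9 panels in 5 columns, 5.4 each;
- over 3 years: 48 × 592/1,095 = 26.0 in 7 columns, 3.7 each;
- over 5 years: 48 × 958/1,825 = 25.2 in 11 columns, 2.3 each.

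The sizes of the ERA and PsA sets are not given. Take exit probability 48/225 = 0.213 spread over 3 years. The chance that a window of 59 to 92 days is empty is (1 − 0.213 × days/1,095)^N. This is 83 to 89% for N = 10, 70 to 79% for N = 20, and 49 to 63% for N = 40.

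**5. Do schedule-matched windows alone rescue the exit values?** Put boundaries midway between scheduled target days and keep the closest-to-target rule. The Month 21 window (Days 591-683) then splits at Day 637:
- Days 591-637 (47 days) go to Month 18, where the child normally has a closer scheduled value, so the exit value is dropped.
- Days 638-683 (46 days) go to Month 24, where the exit value is kept.

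Over Months 15 to 57, the days on which it is kept are 4 × 45 + 4 × 46 = 364 of 732, or 49.7%. About half of these exit values would still be lost.

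**The case against.** **Other wording narrows the display.** Protocol Section 9.2.2 limits efficacy summaries to visits where the measure is taken. SAP 3.2 lists ERA/PsA change at various visits, in contrast to the other endpoints. A sensible programmer might tabulate scheduled months only. This softens the point, but SAP 6.2 and Appendix 1.12 do not say so, and on that reading the exit values would appear only in the listings.

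**A reader might infer that these columns show treatment failures only.** The documents do not support that. Under protocol Appendix 15, participation also ends administratively, for example after first pJIA approval for children from A3921103 and A3921104. Unplanned visits and unscheduled laboratory tests are allowed, including triglycerides for suspected MAS. Late drift adds scheduled visits. Many ERA/PsA columns may be empty.

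**The consequence is limited.** This stands. The study is descriptive, with no hypotheses (SAP 5.1), and the number evaluated is shown. The efficacy plots in SAP 6.2 cover only sJIA1, sJIA2 and pJIA, so no ERA/PsA curve is drawn. Laboratory tables follow sponsor standards that are not in the documents, so the exact lipid layout is unknown.

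**Conclusion.** The point holds as a reporting defect. By nominal month, 20 of 41 ERA/PsA windows and 26 of 41 lipid windows have no scheduled assessment, and no rule covers the exit records that land there. Followed as written, these columns are empty or hold a few exiting children, and should not be read as time course on treatment.

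The window counts need no assumption beyond nominal months, and drift leaves them unaffected through Month 84. The figures per column do rest on assumptions: even exit times, the 48 exits known at the 2019 cutoff, and a panel at every exit. Later administrative endings would raise them. Section 6.2.6 asks for an early termination visit after a safety discontinuation only where possible, which would lower them.

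It would go too far to conclude that half the results are biased by treatment failure, or that any formal conclusion changes.

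**What to change.** In SAP Appendix 1.12, add a window table for each schedule, as already exists for Tanner Stage, with boundaries midway between scheduled target days:
- **ERA/PsA:** Month 3 to Day 135, Month 6 Days 136-272, Month 12 Days 273-455, Month 18 Days 456-637, and so on.
- **Lipids:** Months 6, 12 and every 6 months to 60 in the same way, then Months 72, 84, 96, 108 and 120 with yearly windows.

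Add a separate End of Study/Early Termination row using each child's exit value, so that the closest-to-target rule does not remove it from the tables. Leave triglycerides drawn for suspected MAS out of the by-visit lipid tables.

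Midpoint boundaries also return on-time Month 114 and 120 visits to their own columns: Days 3420 and 3600 lie beyond the midpoints at Day 3375 ((3285 + 3465)/2) and Day 3557 ((3465 + 3650)/2 = 3557.5).

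The cost is an added window table, one row and minor programming, with no new data and no change to care. Some exit values will sit about 3 months from their label, and up to about 6 months for lipids before Month 6 or after Year 5.
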